#### *Pregnancy and breastfeeding*

There are no adequate and well-controlled trials of neridronic acid in pregnant or lactating women. Although there are no data on fetal risk in humans, bisphosphonates do cause fetal harm in animals, and animal data suggest that uptake of bisphosphonates into fetal bone may be greater than into

maternal bone. Therefore, neridronic acid should not be administered during pregnancy and lactation and as a result, pregnant or lactating women are excluded from participation in this trial.

Women of child-bearing potential must have a negative urine  $\beta$ -HCG pregnancy test at the Enrollment Visit and prior to each infusion of IMP. Trial subjects must use contraception as defined in inclusion criterion 6.

#### **Risks related to acetaminophen and calcium and vitamin D supplementation**

High doses of acetaminophen may cause hepatotoxicity and can lead to liver failure. Subjects who take acetaminophen for prevention or relief of symptoms of the acute phase reaction during the treatment periods will be reminded that the total dose must not exceed 4 g/day and that caution should be exercised since acetaminophen may be present in many over-the-counter drugs, particularly analgesic medications.

Recommended daily doses of calcium and vitamin D are lower than the tolerable upper intake level, at which there is no risk to healthy individuals (Ross et al. 2011; Rosen et al. 2012). Short courses of high doses of vitamin D are anticipated to pose no significant risk to trial participants.

#### **General risks**

Subjects will be regularly monitored for any changes in their medical status, e.g., vital signs, ECG parameters, and laboratory values, during the trial (see Section 12.1 for overall volume of blood samples).

Blood sampling may cause pain or bruise at the site where the blood is taken due to insertion of the needle. No other invasive procedure is planned. The total volume of blood to be collected and the planned sampling frequency do not pose any clear risk and are considered justifiable in the context of the trial and its duration.

#### **Conclusion**

As there are currently no FDA or EMA approvals for specific pharmacological treatments for CRPS, which is a severe pain condition with limited effective treatment options, the potential for benefit of neridronic acid is considered to outweigh the potential risk in this population. The need for controlled efficacy and safety trials of potential new treatments for CRPS justifies this trial on moral and ethical grounds.

## **9 SUBJECT ENROLLMENT AND TRIAL DISCONTINUATION**

### **9.1 Subject enrollment procedure**

Subjects will be screened to identify subjects who could potentially be enrolled into the trial. Potentially eligible subjects will be asked to enroll into the trial by giving written informed consent.

If required by applicable regulatory requirements, the (principal) investigator must keep suitable logs of the subject enrollment procedure.

Subjects who were enrolled in KF7013-01 but were not allocated to treatment (i.e., did not receive any treatment with IMP) or who only received placebo may be eligible if they satisfy all inclusion and exclusion criteria in Section 1.3.

Re-enrollment will be permitted (once), upon approval by the sponsor, for subjects with technical reasons for enrollment failure (e.g., inadequate time period for stabilization of treatment; inadequate time from discontinuation of a prohibited medication or treatment). No subject who received infusion of IMP, even a partial infusion, is allowed to be re-enrolled. Re-enrollment of subjects who did not meet inclusion criteria related to the diagnosis of CRPS and the baseline pain level is not allowed. Re-enrolled subjects must fulfill all inclusion and exclusion criteria in the current protocol. If a subject is re-enrolled, a new subject ID will be assigned and all enrollment procedures will be performed under the new subject ID.

## **9.2 Inclusion/exclusion criteria**

The trial population must comply with the inclusion/exclusion criteria given in Section 1.3.

Subjects will only receive IMP if documentation is available showing that they comply with all of these criteria.

## **9.3 Subject discontinuation from the trial or IMP**

Once a subject enrolls in this trial, whilst protecting subject safety, the trial site should make every effort to retain the subject for the planned duration of the trial.

A subject may withdraw consent at any time.

### **9.3.1 Subject discontinuation from the trial**

All bisphosphonates have a long retention time in bone, and duration of efficacy is related to their persistent effects on bone turnover, specifically the inhibition of activation of bone resorption (Al Nofal et al. 2015; Naylor and Eastell 2012; Jung and Lein 2014). Collection of follow-up data is important for characterizing the safety and efficacy of neridronic acid. Subjects who receive any treatment, even a partial infusion, should be encouraged to remain in the trial for the full duration for follow-up safety and efficacy assessments.

Under certain situations, discontinuation from the trial may be required or be in the best interest of the subject from a risk/benefit perspective. [Table 1](#) lists mandatory and optional reasons for discontinuation from the trial.

Table 1: Reasons for compulsory and optional discontinuation of subjects

Reason	Discontinuation from trial	
	Compulsory	Optional
Enrollment failure (i.e., subject was not allocated to treatment due to failure to meet inclusion or exclusion criteria and did not receive IMP).	X	
Subject withdrawal of consent (the reason for withdrawal must be specified).	X	
Subject death.	X	
Subject loss to follow-up (i.e., no further contact with the subject is possible).	X	
Sponsor decision to discontinue the subject.	X	
Technical reasons (e.g., site is no longer able to function or participate in the trial, and the subject is too remote from other site locations).		X
Sponsor decision to terminate the trial.	X	
Other reasons (e.g., subject becomes engaged in litigation related to their disability from CRPS in which monetary gain may affect their objective participation in the trial).		X

CRPS = complex regional pain syndrome, IMP = investigational medicinal product.

### 9.3.2 Subject discontinuation from the IMP

Discontinuation of IMP applies only to Treatment Period A or Treatment Period B. Subjects who are discontinued from IMP should not be discontinued from the trial except for reasons indicated in [Table 1](#). Subjects who are discontinued from IMP should be encouraged to remain in the trial for their own safety and for the integrity of the trial.

Subjects must be evaluated prior to each infusion of IMP. The investigator must permanently or temporarily discontinue treatment with IMP for any reasons listed in [Table 2](#). The investigator may decide to temporarily discontinue a subject from receiving IMP for other reasons (e.g., if further assessments may be helpful to assure safety of the subject). The investigator may also choose to permanently discontinue a subject from treatment if they believe that continued exposure of the subject to neridronic acid may pose an undue risk to the subject, e.g., due to particular adverse events or due to deterioration in the subject's health for reasons related or unrelated to the treatment.

In situations where treatment is temporarily discontinued, Treatment Period A or Treatment Period B may be extended to a maximum of 21 days (for details, see footnote b) in [Section 1.6.1](#) and [Section 1.6.2](#)).

Table 2: Reasons for permanent and temporary discontinuation of subjects from IMP

Reason	Discontinuation from IMP	
	Permanent	Temporary
Symptomatic hypocalcemia.		X
Serum calcium <7.8 mg/dL (<1.95 mmol/L). The subject may resume treatment following investigator assessment and a repeat serum calcium value above this limit (albumin-corrected serum calcium should be considered if serum albumin is below 3.5 g/dL).		X
Clinical signs of dehydration (e.g., dizziness, palpitations, confusion).		X
Test results suggestive of a possible change in renal function:		

 
• A persistent <math>\geq 25\%</math> decrease in the eGFR from the last value observed prior to the first IMP administration, based on repeated central laboratory results from blood samples obtained at least 1 week apart a.
 
	X	

 
• A <math>\geq 25\%</math> decrease in the eGFR from the last value observed prior to the first IMP administration. If a repeated measurement of eGFR is within 75% or more of the respective value, the subject may resume treatment a.
 
		X

 
• A persistent urinary ACR based on an initial value <math>>300</math> mg/g (semi-quantitative dipstick or quantitative urinary albumin and creatinine data from the central laboratory) and on a second value <math>\geq 150</math> mg/g (quantitative urinary albumin and creatinine data from the central laboratory) from urine samples obtained at least 1 week apart.
 
	X	

 
• A urinary ACR <math>>300</math> mg/g based on the results of the semi-quantitative dipstick or quantitative data from the central laboratory. The subject may resume treatment if quantitative urinary albumin and creatinine data from the central laboratory indicate a urinary ACR value <math><150</math> mg/g from urine samples obtained at least 1 week apart.
 
		X

 
• A persistent eGFR <math><30</math> mL/min/1.73 m^2 based on repeated quantitative data from the central laboratory, with urine samples obtained at least 1 week apart.
 
	X	

 
• An eGFR <math><30</math> mL/min/1.73 m^2. If a repeated measurement of eGFR is <math>\geq 30</math> mL/min/1.73 m^2, the subject may resume treatment.
 
		X
An average QTcF interval of $>500$ ms based on triplicate ECGs, or average QTcF interval of $>480$ ms with a concurrent increase in average QTcF interval $>60$ ms relative to the average of triplicate ECGs obtained at Visit 1.	X	
Pregnancy.	X	
Development of hypersensitivity to the IMP.		X
Signs or symptoms of ocular inflammation: b		

Reason	Discontinuation from IMP	
	Permanent	Temporary
• Resolution of signs and symptoms within 5 days.		X
• Persistent or recurrent signs and symptoms.	X	
Newly occurring risk factors for osteonecrosis of the jaw (e.g., need for emergency dental surgery).	X	
Any other adverse event causing a significant deterioration in subject's health.		X
Major protocol deviations (e.g., serious non-compliance with protocol procedures, unsafe use of forbidden medication, abuse of illicit drugs, or other reckless behavior during the trial that may jeopardize the subject's safety or safety of other subjects or site staff).	X	

a) Not applicable if no eGFR value after first IMP administration is available. For both treatment periods, the last value observed prior to first IMP application in Treatment Period A will be used for calculating the decrease in eGFR.

b) Subjects should be assessed for ocular inflammation by the investigator prior to each infusion (signs and symptoms include eye redness and irritation, blurred vision, eye pain, and sensitivity to light). Subjects with signs or symptoms of ocular inflammation should be temporarily suspended from treatment. Subjects with resolution of signs and symptoms within 5 days may resume treatment. Subjects with persistent or recurrent signs and symptoms of ocular inflammation must be discontinued from IMP and undergo an ophthalmologic examination.

ACR = albumin to creatinine ratio, eGFR = estimated glomerular filtration rate, ECG = electrocardiogram, IMP = investigational medicinal product, QTcF = corrected QT interval (according to Fridericia's formula).

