  - Serum calcium or magnesium outside of the central laboratory's reference range, despite appropriate supplementation between Visit 10 and Visit 11, based on the last central safety laboratory data obtained prior to Visit 11. One repeat laboratory test is allowed.
  - Vitamin D deficiency prior to IMP re-allocation, defined as a 25(OH)D level less than 30 ng/mL (75 nmol/L), based on the last central safety laboratory data obtained prior to Visit 11, i.e., inability to normalize 25(OH)D levels to at least 30 ng/mL (75 nmol/L) despite appropriate supplementation between Visit 10 and Visit 11. Two repeat laboratory tests are allowed (with a minimum interval of 3 days).

- Elevated aspartate aminotransferase or alanine aminotransferase greater than 2-fold upper limit of normal, based on central safety laboratory data obtained at Visit 10, or current evidence of chronic liver disease. A single repeat laboratory test is allowed.
- No other criterion for trial and/or IMP discontinuation is met.

The subjects and investigators will stay blinded to the treatment that the subject received in Treatment Period A.

If, at Visit 11, the criteria to continue into Treatment Period B are not met, the subjects will not receive any further IMP infusion and will continue with the follow-up visits Visit 16 and Visit 17. Subjects can only start Treatment Period B at Visit 11.

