#### **9.3.3.2 Handling of subjects discontinued from the IMP but not from the trial**

Subjects who are temporarily suspended from IMP may undergo abbreviated visits for safety assessments to support a decision to continue treatment or permanently discontinue IMP. Subjects

who are permanently discontinued from IMP should proceed to Visit 6 (for Treatment Period A) or Visit 15 (for Treatment Period B) at approximately 4 days after the last infusion, if possible; Visit 7 or Visit 16, respectively, and subsequent visits will proceed according to the original visit schedule (relative to Visit 2).

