#### **11.1.2 Treatment Period A**

Infusion visits should be separated by 3-day intervals to the extent possible (i.e., Day 1, Day 4, Day 7, and Day 10). Infusion visits on consecutive days are not allowed. The full dosing period must not exceed 21 days from the first infusion (Visit 2). To facilitate scheduling, the interval between infusion visits may be adapted, provided the 21-day time period is not exceeded and discontinuation criteria can be assessed. In case of suspension of treatment due to a suspected safety concern or a visit scheduling difficulty, resumption of treatment is allowed upon resolution of findings, with sponsor agreement.

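### Hypersensitivity to the IMP requires only a temporary stop, with no mandatory permanent stop for a confirmed or serious reaction and no express bar to Treatment Period B

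*Protocol*

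**What the plan says.** Protocol Section 9.3.2 makes Table 2 mandatory: "The investigator must permanently or temporarily discontinue treatment with IMP for any reasons listed in" the table. The column decides which kind of stop applies. Hypersensitivity has a single row, "Development of hypersensitivity to the IMP", marked Temporary, and nothing is said about when dosing may restart.

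Other rows are graded. A fall in eGFR of at least 25% is a temporary stop at first and a permanent one if persistent, "based on repeated central laboratory results from blood samples obtained at least 1 week apart". Ocular inflammation is temporary if it clears within 5 days and permanent for "Persistent or recurrent signs and symptoms".

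Outside the table, Section 9.3.2 gives discretion: "The investigator may also choose to permanently discontinue a subject from treatment" where continued exposure is judged an undue risk. Sections 11.1.2 and 11.1.4.2 add a general rule for treatment that has been suspended: "resumption of treatment is allowed upon resolution of findings, with sponsor agreement".

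For the second course, Section 1.3.3 re-applies a selected list of exclusions at Visit 11 and closes with a catch-all, "No other criterion for trial and/or IMP discontinuation is met". Section 9.3.3.2 describes permanent stops period by period: subjects "who are permanently discontinued from IMP should proceed to Visit 6 (for Treatment Period A) or Visit 15 (for Treatment Period B"), and later visits then follow the original schedule.

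**The concern.** That a reaction has resolved does not show that the next infusion will be tolerated. Resolution is a sensible test for dehydration or low calcium, but a poor one for hypersensitivity. Yet the only binding instruction for a subject who reacts is to pause. Nothing in the protocol makes the stop permanent once the reaction is confirmed, or if it was serious.

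The same gap recurs at Week 26. Period B always gives neridronic acid, and Section 1.3.3 keeps the investigator blinded to the Period A allocation. A site deciding on a second course for a Period A reactor does not know whether the reaction was to active drug or placebo. Section 10.4.3 allows the code to be broken if that would change management, but does not require it.

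At stake is the possible re-exposure of a sensitised subject, either later in the same course or in a new course of up to four infusions.

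**Working it through.** The defect is one of wording, so the check is mainly a side-by-side reading. The arithmetic prices the remedy and is not evidence for the defect.

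**1. Tally of Table 2.** There are 17 marked rows.

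- Permanent, 8: persistent eGFR fall of at least 25%; persistent ACR; persistent eGFR below 30; QTcF; pregnancy; persistent or recurrent ocular inflammation; new risk factors for osteonecrosis of the jaw; major protocol deviations.
- Temporary, 9: symptomatic hypocalcemia; low serum calcium; dehydration; eGFR fall; ACR above 300 mg/g; eGFR below 30; hypersensitivity; ocular inflammation resolving within 5 days; any other adverse event with significant deterioration.

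Four of the 9 Temporary rows have a Permanent counterpart: eGFR fall, ACR, eGFR below 30 and ocular inflammation. Five do not, and hypersensitivity is one of them. The general adverse-event row is also Temporary only, so it supplies no mandatory permanent stop for a serious reaction.

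**2. Whether Temporary implies possible resumption.** Sections 9.3.2 and 10.2 let the dosing period be extended, to at most 21 days, when treatment is temporarily discontinued. A Temporary mark therefore contemplates restarting. As the hypersensitivity row sets no condition of its own, what remains is the general rule of resolution plus sponsor agreement.

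**3. Section 1.3.3 against the 20 entry exclusions in Section 1.3.2.** Eight are re-applied in whole or part: criteria 1 (renal), 2 (calcium, magnesium), 3 (vitamin D), 4 (QTcF, potassium, cardiac), 5 (torsades drugs), 8 (dental), 16 (liver) and 19 (forbidden treatments). Criterion 7, which covers allergy or hypersensitivity to neridronic acid, is not among them, and Section 1.3.3 nowhere mentions hypersensitivity. The catch-all is in the present tense. It may bar anyone who developed hypersensitivity, or only someone who still meets a criterion at Visit 11. Since it points back to a Temporary-only row, a resolved Period A reaction is not expressly excluded. Repairing Table 2 alone would not settle this: a subject permanently stopped in Period A still attends Visit 11, and no text says that the stop carries over.

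**4. Cost of the remedy in power.** Inputs from Section 1.5.1: difference 1.0, SD 2.0, one-sided α = 0.025, and 86 per arm required or 90 per arm planned. For a two-sample t test the noncentrality is δ / (SD·√(2/n)), on 2n − 2 degrees of freedom.

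- The protocol's own figure: n = 86 gives 1.0 / (2.0·√(2/86)) = 3.279 and power 90.3%, which agrees with the stated minimum of 90%.
- Planned size: n = 90 gives 1.0 / (2.0·√(2/90)) = 3.354 and power 91.6%.

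As a worst case, assume that k of the 90 active subjects stop in Period A and lose the whole effect. The mean difference becomes 1.0·(1 − k/90):

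| k | Difference | Power |
|---|---|---|
| 0 | 1.000 | 91.6% |
| 1 | 0.989 | 91.0% |
| 2 | 0.978 | 90.4% |
| 3 | 0.967 | 89.7% |

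These figures ignore the optional futility look.

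**The case against.** Three arguments on the other side deserve weight.

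First, the row can be read narrowly. Hypersensitivity is a state rather than an episode, and Section 10.2 requires the criteria to be checked before every infusion, so a confirmed reactor would keep meeting the criterion and never be dosed. The general resumption rule also speaks of a suspected safety concern, and the rows that foresee resumption mostly say so themselves. This reading is possible but the text does not compel it. The extension of dosing after a temporary stop points the other way, and a stopping rule should not depend on which reading a site adopts. It is fair to say that the protocol does not direct re-exposure; it fails to preclude it.

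Second, there are real safeguards: sponsor agreement to resume, investigator discretion to stop, the investigator's decision on intolerable serious events (Section 12.4.1), 24-hour reporting of serious events, compulsory withdrawal if the sponsor so decides (Table 1), emergency code-break, and the duty in Section 8.2 to follow the investigator's brochure. They make unsafe re-dosing less likely. Within the protocol, each is a case-by-case decision, and none makes stopping mandatory for a confirmed or serious reaction. The brochure is not available here and nothing is assumed about its content.

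Third, for Period B, the catch-all together with the suspension check at Visit 11 may already bar a reactor. That is one of two readings, so this part is a clarification. A temporary hold while a suspected reaction is assessed is entirely defensible and should stay. Nor is it a contradiction that exclusion criterion 7 is stricter than Table 2, since entry limits in this protocol are generally tighter than stopping limits.

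**Conclusion.** The concern holds. Table 2 sets a binding rule for hypersensitivity that stops at a pause, although the same table grades four other problems up to a mandatory permanent stop. Section 1.3.3 does not expressly keep a Period A reactor out of a course that is always active drug.

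The size of the harm is unknown, because the protocol gives no rate for such reactions. The existing discretionary gates reduce the risk, so this should be corrected but does not call the design into question. The conclusion rests on the protocol text alone and on reading the hypersensitivity mark as lying in the Temporary column. The neighbouring rows support that reading, with pregnancy as Permanent and serum calcium as Temporary.

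**What to change.** Two edits by amendment:

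- **Table 2, Section 9.3.2.** Replace the single row with two. Suspected hypersensitivity to the IMP, until assessed and ruled out: Temporary. Confirmed or serious hypersensitivity reaction to the IMP: Permanent.
- **Section 1.3.3.** Add to the listed exclusions: hypersensitivity reaction to IMP in Treatment Period A, unless ruled out on assessment.

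Suspected reactions that are ruled out can still resume. The price is that a few subjects, some of them on placebo, lose further infusions. Section 9.3.2 encourages them to stay in the trial, and one infusion, even partial, keeps them in the Full Analysis Set, so the treatment-policy estimand is unaffected. Even on the worst-case assumption above, the power loss for 1 to 3 active subjects is at most 91.6 − 89.7 = 1.9 percentage points. The Section 1.3.3 line acts at Week 26 and cannot touch the Week 12 primary endpoint; Period B is analysed descriptively only.

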### **9.3.3 Procedure for the handling of discontinued subjects**

#### **9.3.3.1 Handling of subjects who discontinued from the trial**

The principal investigator must document any discontinuation of a subject and inform the sponsor. Where applicable, the relevant IECs or IRBs must be informed with a detailed written explanation.

The following must be done for **all** discontinued subjects, including those who withdrew informed consent:

- Document the main reason for discontinuation from the trial.
- Ensure that all data collected until the time of discontinuation is transferred to the eCRF.
- Complete any other trial-related formalities, e.g., those related to discharge from the trial site.
- For subjects withdrawing consent, document in the source data the date and time of withdrawal.
- If possible, perform an Early Termination Visit, with procedures identical to Visit 17. Subjects who withdraw consent and agree to perform the Early Termination Visit must document their approval in writing.

